3.4 Endpoints

All codes relevant to abstracting diagnostic, drug, and laboratory data appear in Appendix 1.

3.4.1 Use of rosiglitazone in persons with contraindications

These outcomes will be ascertained using the Danish National Registry of Patients in Denmark and using the GPRD's Event File in the UK.

Using data on inpatient and outpatient hospitalizations, we will ascertain proportions of rosiglitazone users with the following conditions recorded before the first prescription for rosiglitazone (since 1977 in Denmark, since 1987 in the UK):

- History of heart failure or ischemic heart disease;
- History of acute coronary syndrome;
- History of peripheral vascular disease
- History of acute myocardial infarction;
- History of hepatic impairment (moderate to severe liver disease);

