The present study was commissioned by the European Medicines Agency (EMA), following the suspension of rosiglitazone preparations in the European Union. EMA wishes to retrospectively examine the impact of risk minimisation actions in the European Union (such as warnings, scientific publications, and regulatory decisions) on utilization of rosiglitazone and on the condition of rosiglitazone-using patients with type 2 diabetes (the target population).

2 Specific aims

The specific aims of this study are as follows:

- To describe trends in patterns of utilisation of rosiglitazone-containing preparations over time, in particular, in response to external events, such as scientific and media publications, EMA's press releases, or EMA's regulatory decisions aimed at risk minimisation;
- To examine the extent of use of rosiglitazone-containing preparations in persons with potential contraindications;
- To examine the extent of use of rosiglitazone-containing preparations in persons outside the primary indication (off-label use);
- To examine risk of acute drug reactions among patients who switch from alternative antidiabetic therapies to rosiglitazone preparations or vice versa;
- To examine glycaemic control and other objective parameters of disease among patients who switch from alternative antidiabetic therapies to rosiglitazone preparations or vice versa.

3 Methods

3.1 *Setting and study population*

This study will be conducted in Denmark and in the United Kingdom (UK).

In Denmark, the source population includes residents of the country's North and the Central regions, with combined population of about 1.8 million, or approximately 33% of the population. Denmark is a welfare state, with universal, tax-funded access to all medical services, including reimbursement for prescribed medicine. Many medical services rendered in Denmark have been routinely and prospectively recorded, on patient level, for the past several decades in population registries; data linked from these registries will be used in the present study.¹⁴

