3.4.2 Off-label use

These outcomes will be ascertained using AUPD or the Danish National Registry of Patients in Denmark and using the GPRD's Event File or Drug File in the UK. Off-label use will be defined as prescription of rosiglitazone dispensed by/issued to:

- Patients aged 16 years or younger at the time of any rosiglitazone prescription;
- Patient with concomitant use of insulin, defined as at least one prescription for insulin in between the first and last prescription for rosiglitazone²;
- Patients diagnosed with type 1 diabetes mellitus;

- Women with gestational diabetes without evidence of pre-gestational diabetes (UK only);
- Women with polycystic ovary syndrome (UK only)

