3.6.2 Contraindications for use and off-label use

Prevalence of contraindicated or off-label use will be examined according to calendar time, where events marking relevant scientific publications and regulatory decisions will be marked. We will

report the number and proportion of patients prescribed rosiglitazone who had a diagnosis consistent with a contraindication for rosiglitazone use or with off-label use as defined in the Methods. We will provide the proportions in each country and over time. We will follow the analytic methods described above, provided that the sample size is large enough. At a minimum, use by patients with the additional contraindications (ischemic heart disease and/or peripheral vascular disease) listed in the 2008 press release¹⁰ will be examined in the periods before and after the publication of the press release including any prior diagnosis of liver disease, ischemic heart disease, cardiac failure, or acute coronary syndrome.

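### Contraindication status is fixed at the first rosiglitazone prescription, so continued prescribing after a diagnosis made on treatment is never counted in the calendar-time and before/after-2008 analyses

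*Protocol*

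**What the plan says.** The second aim in Protocol section 2 is "To examine the extent of use of rosiglitazone-containing preparations in persons with potential contraindications". It is not limited to use at initiation.

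Section 3.4.1 sets the endpoint as the proportion of rosiglitazone users with "conditions recorded before the first prescription for rosiglitazone". Nothing there updates this status later.

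Section 3.6.2 states: "Prevalence of contraindicated or off-label use will be examined according to calendar time". It reports the number and proportion of patients prescribed the drug who had "a diagnosis consistent with a contraindication for rosiglitazone use or with off-label use as defined in the Methods", which leads back to 3.4.1. As a minimum, use by patients with the contraindications added in 2008 (ischemic heart disease and/or peripheral vascular disease) "will be examined in the periods before and after the publication of the press release including any prior diagnosis of liver disease" and other listed conditions. The text does not say prior to what.

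The off-label criteria in section 3.4.2 use other anchors. Age is judged by "Patients aged 16 years or younger at the time of any rosiglitazone prescription". Insulin co-use is "at least one prescription for insulin in between the first and last prescription for rosiglitazone".

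**The concern.** The study was commissioned to examine the impact of risk minimisation actions. For an action that adds contraindications, a central question is what happens to people already on the drug who have, or acquire, one of the listed conditions. A status fixed at the first prescription answers this only for those diagnosed before they started.

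Take someone who starts in 2003, is diagnosed with ischaemic heart disease in 2006 and is still prescribed rosiglitazone in 2009. Under 3.4.1 this person counts as a user in 2009 but not as a contraindicated one. If the same person stops in 2008 because of the new contraindication, that response is equally invisible. The protocol foresees such diagnoses, since section 3.4.3 lists acute myocardial infarction among the new events to look for after a switch to rosiglitazone.

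The missing reference date in 3.6.2 adds a practical risk. Section 4 gives the Danish and UK analyses to different groups. If one group reads the prior diagnosis as prior to first use and the other as prior to a prescription in the period, the proportions by country are not comparable.

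**Working it through.** The protocol states no expected prevalence, incidence or sample size for this endpoint, so there is no figure of its own to reproduce. The check has three parts.

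**1. The rule.** Section 3.6.2 takes its denominator from patients prescribed rosiglitazone over calendar time, and its definition of a contraindication from the Methods. Section 3.4.1 dates the diagnosis before the first prescription. Together they place an on-treatment diagnosis in the denominator only. This needs no assumption.

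**2. Room for it to matter.** From the dates in section 3.6.1, counting both end days and dividing by 365.25:
- Period 1, 1 July 2000 to 23 May 2007: 6.89 years
- Period 2, 24 May 2007 to 24 January 2008: 0.67 years
- Period 3, 25 January 2008 to 22 September 2010: 2.66 years

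A user entering Period 3 may be up to 6.89 + 0.67 = 7.56 years past the first prescription. A user late in Period 1 may also be years past it, so undercounting is not confined to the later period.

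**3. Illustration under assumed inputs.** None of these comes from the protocol: prevalence at first prescription p0 = 10–20%, equal in both periods; incidence of a first listed diagnosis r = 1–4% per year; mean time since first prescription t = 1–2 years before and 2–4 years after 2008; nobody stops because of a diagnosis.

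Updated share: p(t) = p0 + (1 − p0)(1 − exp(−r·t)). Share of contraindicated users missed by fixed status: 1 − p0/p(t).

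With p0 = 10%, r = 2%, t = 2 and 4:
- before: 0.10 + 0.90 × (1 − exp(−0.04)) = 13.5%; missed 1 − 0.10/0.135 = 26%
- after: 0.10 + 0.90 × (1 − exp(−0.08)) = 16.9%; missed 1 − 0.10/0.169 = 41%
- change: +3.4 points with updated status, 0 with fixed status

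| p0 | r per year | t before / after | updated before / after | missed before / after | change hidden |
|---|---|---|---|---|---|
| 20% | 1% | 1 / 2 | 20.8% / 21.6% | 4% / 7% | 0.8 points |
| 10% | 2% | 2 / 4 | 13.5% / 16.9% | 26% / 41% | 3.4 points |
| 10% | 4% | 2 / 4 | 16.9% / 23.3% | 41% / 57% | 6.4 points |
| 10% | 2% | 2 / 2 | 13.5% / 13.5% | 26% / 26% | 0.0 points |

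The last row shows that with equal time since first prescription the levels are too low but the difference is unaffected.

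**Allowing for stopping.** Suppose 1,000 users, 100 with a pre-start and 100 with an on-treatment diagnosis, and half of each group stops after the warning. True prevalence goes from 200/1,000 = 20% to 100/900 = 11.1%, a fall of 8.9 points. Fixed status goes from 100/1,000 = 10% to 50/900 = 5.6%, a fall of 4.4 points. The relative fall is 44% in both, but the absolute effect now looks smaller than it was. The direction of distortion is therefore not determined.

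**The case against.** A reader might infer that the 2008 comparison is invalid. It is not. People starting before and after the change are classified correctly, and continued use or stopping among those with a pre-start diagnosis is visible.

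A reader might also infer that the 2008 action will look more effective than it was, and increasingly so with calendar time. That follows only if diagnoses accumulate, nobody stops because of them, and time since first prescription is longer after 2008. The protocol gives no split between starters and continuing users, the error depends on time since first prescription rather than on calendar time itself, and the stopping example reverses the direction. The percentages above cannot serve as estimates. Nor does the protocol call the uncounted patients appropriately treated; it only leaves them out of the contraindicated group.

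The best textual defence is that section 3.6.2 refers to any prior diagnosis without a date, and follows the earlier monthly and sliding-window methods, so a time-updated reading is possible. This does not rescue the rule. If the reference is the first prescription, the gap stands; if it is a prescription in the period, 3.6.2 contradicts 3.4.1. The text has to change either way.

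On insulin, section 3.4.2 gives a person-level definition and does not say how it is spread over calendar time, so backdating is one reading, though a natural one. That is why it is secondary here.

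**Conclusion.** The point holds. The stated rule does not measure the extent of use named in the aim: prescribing that continues after a contraindication arises on treatment is never counted. The level is understated in any period in which such diagnoses occur, and the response of prescribers to a new diagnosis cannot be observed.

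The before/after difference is affected only so far as time since first prescription, incidence on treatment, or stopping after diagnosis differs between periods. The documents settle none of these. Under the assumed ranges without stopping, fixed status misses 4–41% of contraindicated users before 2008 and 7–57% after, and hides a change of 0.8 to 6.4 points when time since start is longer after 2008, or 0 when it is equal. These figures show what is possible and do not forecast the bias.

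The whole-span insulin flag is a lesser mismatch of the same kind: a single insulin prescription in 2009 can mark the same patient's rosiglitazone use in 2004 as off-label, which does not suit reporting by calendar time.

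**What to change.** - In 3.4.1 and 3.6.2, state one reference date for the calendar-time and 2008 analyses. Among persons with a rosiglitazone prescription in the month, window or period, count those with a listed diagnosis dated before that prescription.
- Keep the version based on diagnoses before the first prescription as a separate, labelled result for initiators.
- Name the reference date for the prior diagnoses in the 2008 comparison in 3.6.2, so that both countries apply the same rule.
- Secondary: in 3.4.2, for calendar-time reporting, assign insulin co-use to the period in which insulin and rosiglitazone prescriptions actually overlap, instead of to the whole span of rosiglitazone use. The width of any overlap window is for the study team to choose and state.

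The cost is a rewording of these sections and one extra date comparison per prescription. The existing rule already needs dated diagnoses and prescriptions, so no new data are required.

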In the UK, the study will be conducted based on data from the General Practice Research Database (GPRD). The GPRD is an ongoing longitudinal database that collects data from over 350 general practices in the UK since 1987. The UK provides a unique medical environment to create a computerized medical data resource for medical epidemiological research for two main reasons: a) the primary health care system comprehensively covers the UK population; b) the information on all relevant medical care is located in the offices of the general practitioners (GPs), who function as "gatekeepers" for hospital and specialist referrals in the UK health system. The GPRD contains information on more than 6 million patients, of whom 3.5 million are currently registered, and a

cumulative follow-up time of more than 40 million person-years. It covers 6% of the UK population; this sample is representative with respect to age, gender and race/ethnicity distribution.

The study population will include, in both countries, diabetic patients treated with oral glucose lowering drugs between 1 January 2000 and 1 January 2011. This period covers the time from the approval of rosiglitazone for use in the European Union, in July 2000, until the decision by the European Medicines Agency to suspend the drug, on 23 September 2010. The study period also includes a pre-approval and a post-suspension periods to allow examination of drug utilization patterns in response to these events.

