6.1 Denmark

The Aarhus University Prescription Database records all reimbursed prescriptions dispensed in community pharmacies of the North and Central Denmark Regions – 2 of the 5 Danish regions, with combined population of 1.8 million, or 30% of the entire Denmark's population. Prescriptions for oral glucose-lowering medications are eligible for general reimbursement and are therefore recorded in this database; more than 98% of antidiabetic prescriptions are dispensed in the primary sector,² and are therefore expected to be recorded in this database. Recorded information includes the Anatomical Therapeutic Chemical classification of the drug, date of the dispensation, and unique product number.

Laboratory Information Systems for North and Central Denmark Regions (LABKA) track all hospital-performed laboratory tests, including those sent to hospital laboratories by general practice. The following data are recorded: the test name and IUPAC-code, the result, the measurement unit, the dates of ordering and carrying each test. The current coverage period for the Central Region ~ October 1999 to September of 2009, inclusive, for the North Region from 1997 to 2008, inclusive.

The Danish Central Personal Registry covers the entire Danish population and since 1968 has registered all births, deaths, and migration of Danish residents. This database contains dates of all recorded events and is updated daily.

The Danish Registry of Causes of Death contains information on causes of death, including associated diagnoses. Data have been collected since 1970.

The Danish National Registry of Patients covers the entire Danish population and has registered hospitalizations since 1977, including outpatient visits since 1995. Up to 20 discharge diagnoses are recorded for each hospital contact, using the International Classification of Diseases 10th revision (ICD-10) since 1994 and ICD-8 in the earlier period.

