6.2 United Kingdom

The GPRD data are recorded using multiple data screens or files. These include the registration file, the drug file, the event file, the laboratory file, and files containing additional clinical details:

Registration File This file contains information regarding the registration status of each covered patient. Besides unique identification numbers for each individual, family, and practice, this file includes year of birth, gender, date of registration with the current general practice, most recent registration status (permanent, transferred out, died), and date of death or departure from the practice including reason for departure (where applicable).

Drug File This file contains detailed information on all drugs prescribed by the GP. Drugs are coded with the Multilex coding system, with a specific code for each commercial preparation. Details include the date of each drug prescription, the precise drug formulation and strength, the quantity and the dosing instructions of drug prescribed. In addition, the indication for treatment is required for all new courses of therapy. This classification of indication is done by cross-referencing prescriptions against medical events on the same date. It is worth noting that when patients are initially seen by consultants or in hospital, future drug therapy is directed through the GP and is thus captured by the database.

Event File This file contains all clinically relevant patient diagnoses along with the date of the event. Because the GP is the primary care giver for all patients in the National Health Service, all consultants are required to send a letter to the GP whenever a patient is seen in hospital or by an outpatient specialist, describing the relevant clinical events and final diagnoses. In addition to usual care in the GP office, GPs are required to enter all diagnoses resulting from hospitalizations, consultations, or emergency medical care. Diagnoses and events are coded using the READ code.

Additional Clinical Details File This file contains patient general health/life information such as blood pressure, height, weight, smoking status, alcohol use, cervical smears, and medical procedures. While the GPs are not required to update all of these data fields, information on characteristics such as height, weight, and smoking have been used repeatedly and are available on greater than 70% of the population.

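### Contraindication history runs from fixed start years to the first rosiglitazone prescription, so later starters have more recorded history and a real fall after January 2008 could be masked

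*Protocol*

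**What the plan says.** Section 3.4.1 lists the contraindicating conditions (cardiac, peripheral vascular and hepatic). They are found "Using data on inpatient and outpatient hospitalizations" and count if "recorded before the first prescription for rosiglitazone (since 1977 in Denmark, since 1987 in the UK".

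The data-source sections describe the history actually available:

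- Denmark, section 6.1: the National Registry of Patients "has registered hospitalizations since 1977, including outpatient visits since 1995".
- UK, section 3.1: the database "collects data from over 350 general practices in the UK since 1987". Section 6.2 adds that each patient record holds the "date of registration with the current general practice", and that "GPs are required to enter all diagnoses resulting from hospitalizations, consultations, or emergency medical care", on top of diagnoses from the GP's own care.

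On use of the result, section 3.6.2 says "We will provide the proportions in each country and over time". As a minimum it compares use before and after the 2008 press release, counting any prior diagnosis. For this endpoint the protocol sets no equal look-back, no minimum prior registration and no sensitivity analysis. Section 3.5 does use a fixed look-back of ten years, but only for baseline comorbidity covariates.

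**The concern.** When a look-back opens on a fixed date and closes at the first prescription, its length depends on when the patient started. Of two patients with the same disease history relative to treatment start, the one who starts in 2010 has had about ten more years in which a diagnosis could be recorded than the one who starts in 2000. The recorded proportion can then change over calendar time with no change in prescribing.

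The direction is what makes this important. An effective contraindication should lower the proportion after January 2008, and lengthening history pushes it the other way. The study exists to judge the impact of risk minimisation, and the extent of contraindicated use is one of its stated aims, so a masked fall would bear directly on the conclusion.

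The start years also differ by country and care setting, and the UK source is broader. Levels in Denmark and the UK are therefore not measured on the same footing.

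**Working it through.** The protocol gives no expected prevalence for this endpoint, so there is no figure to reproduce.

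**Step 1: available history.** Inputs are the start years in sections 3.4.1 and 6.1 (1 January assumed) and the period dates in section 3.6.1. L = (date of first prescription − start date) / 365.25. For example, Danish outpatient to 1 July 2000 is 2,008 / 365.25 = 5.5 years, and to 22 September 2010 is 5,743 / 365.25 = 15.7 years.

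| Source | 1 Jul 2000 | 24 Jan 2008 | 22 Sep 2010 | Mid-Period 1 | Mid-Period 3 |
|---|---|---|---|---|---|
| Danish inpatient (1977) | 23.5 | 31.1 | 33.7 | 26.9 | 32.4 |
| Danish outpatient (1995) | 5.5 | 13.1 | 15.7 | 8.9 | 14.4 |
| UK (1987, upper bound) | 13.5 | 21.1 | 23.7 | 16.9 | 22.4 |

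Every source gains 10.2 years across the full span and 5.5 years between the middles of Periods 1 and 3. On any date Danish inpatient history is 10 years longer than the UK maximum (1987 − 1977), and Danish outpatient history is 8 years shorter (1995 − 1987). The UK values are maxima because a patient's usable record may begin at practice registration.

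**Step 2: direction and possible size (assumed inputs).** Hold true prevalence at 20%. Let onset be uniform over the past D years (10, 20, 30) and let an existing condition be re-recorded at rate μ per year (0, 0.05, 0.2). The captured share is 1 if D ≤ L; otherwise it is L/D + (1 − L/D)(1 − e^(−μL)).

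Worked case, UK, D = 20, μ = 0.05, July 2000: 0.675 + 0.325 × (1 − e^(−0.675)) = 0.675 + 0.325 × 0.491 = 0.834, so 16.7% is recorded. In September 2010 L exceeds D and 20.0% is recorded.

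Range of the change from July 2000 to September 2010 over all nine combinations:

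| Source | Smallest change | Largest change |
|---|---|---|
| Danish inpatient | none (20.0 to 20.0) | 15.7 to 20.0 |
| UK | none (20.0 to 20.0) | 9.0 to 15.8 |
| Danish outpatient-only diagnoses | 17.0 to 20.0 | 5.5 to 15.7 |

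The change is upward or zero in every case. Period mid-points give a milder contrast. With D = 20 and μ = 0.05 the UK moves from 18.7% (L = 16.9) to 20.0% (L = 22.4), so a true fall from 20.0% to 18.7% would be recorded as flat.

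**Step 3: would sample size expose or absorb it?** Take a spurious 18% versus 20%, an assumed 80:20 split of the users in section 3.3, and a two-sided 5% test with pooled null variance. Power = Φ[(0.02 − 1.96 SE0) / SE1].

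- UK, 16,000 v 4,000: SE0 = 0.00685, SE1 = 0.00702, power 0.83.
- Denmark, 1,920 v 480: SE0 = 0.01977, SE1 = 0.02025, power 0.18.

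In the UK an artefact of two points would usually look like a real difference.

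**Step 4: an equal window.** If L is the same at every date, the captured share is constant and the artefact is zero in this model. The cost is sensitivity. Of a true 20%, a 5-year window captures between 5/30 × 20 = 3.3% (D = 30, μ = 0) and (0.5 + 0.5 × 0.632) × 20 = 16.3% (D = 10, μ = 0.2). A 10-year window captures 6.7% to 20.0%, but Danish outpatient data cannot supply ten years before 1 January 2005.

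**The case against.** There is a serious case for leaving the definition alone.

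- Section 3.4.1 asks about history of a condition, and all available records answer that most completely. This stands for a single overall prevalence.
- Inpatient and outpatient records are pooled, and Danish inpatient data already reach back 23.5 years in July 2000. Chronic conditions are recorded repeatedly. Appendix 1 also contains UK codes for past angina, old infarction and past heart failure, which recover disease older than the record. All of this stands and can bring the bias close to zero. The UK peripheral vascular and liver lists contain no such history codes.
- Lengthening history produces a smooth drift, and the monthly sliding-window plots can distinguish a drift from a step at a milestone. This protects the plotted trend to a degree. The before/after contrast, which section 3.6.2 makes the minimum analysis, is not protected.
- The only quantitative country comparison, in section 3.6.1, is conditional and concerns change in proportion. Fixed differences between the sources matter less there.

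Three stronger readings are tempting and are not supported. A reader might infer that history lengthens with each further prescription; section 3.4.1 closes it at the first. A reader might take the 2.9-fold growth in Danish outpatient history (15.7 / 5.5) as the likely inflation of the endpoint; it concerns outpatient-only diagnoses, while the endpoint pools inpatient records. A reader might expect contraindicated use to be seen rising; the documents support only an upward bias or none, so a true fall may simply be hidden. In addition, if a period's denominator is all users rather than new starters, earlier starters keep their shorter history and the average gain is smaller than in the table.

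**Conclusion.** The point holds as a bias of known direction and unknown size. Under constant true prevalence, the all-history proportion moves upward or not at all as first prescriptions become later, and nothing in the protocol offsets this. It is potentially largest for Danish outpatient-only diagnoses and the UK, and smallest for Danish inpatient conditions. The years of history follow from the documents. The percentages rest on the assumed prevalence, onset and re-recording rates, and only show what is possible. The analysis most exposed is the comparison before and after January 2008. Section 3.4.1 also implies Danish outpatient history from 1977 that section 6.1 shows does not exist; this needs correcting whatever the size of the bias. The change is worth making because it is cheap and the comparison serves a stated aim.

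**What to change.** 1. Keep the all-available-history proportion as the overall description of contraindicated use.
2. In section 3.6.2, for the calendar-time, before/after-2008 and country comparisons, also report the proportion with a diagnosis in an equal fixed window before the first rosiglitazone prescription. Five years is an example that Danish outpatient data can supply for every starter from July 2000.
3. Limit that analysis to patients with at least that much prior residence (Danish Central Personal Registry) or practice registration (UK Registration File).
4. State that no conclusion about the effect of the 2008 change will be drawn from the all-history trend alone.
5. Correct section 3.4.1 to Danish inpatient records since 1977 and outpatient records since 1995. State that the UK source includes GP-recorded diagnoses and history codes, while the Danish source is hospital contacts only.

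The cost is one date condition, one registration condition and some wording. The fixed window misses older diagnoses (step 4 shows how many it could miss) and excludes some UK patients with short registration. Because UK history codes recorded inside the window can refer to older disease, the two countries' windows would still not be fully equal.
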